4. Urine toxicology screens and breathalyzer. At week 4 and week 8 participants will also take a pregnancy test
5. All participants will additionally be required to obtain a blood draw at the CRC on week 4 and week 8 in order to assess LFTs, glucose and CBC and to quantify medication levels.

Procedures

Outpatient procedures: All AUD women will be required to attend two outpatient visits per week for 10-weeks. All women will take part in Medical Management (MM) and Contingency Management (CM) protocols. All clinicians will be fully trained in these procedures, and educated specifically in the treatment needs of women, including relationship issues, caregiving status, anxiety, mood and eating¹³². In week 10 of treatment a 12-day taper schedule will be implemented¹³³, prior to discharge

Dosing: Dosing will begin at Intake 2 appointment. Women receiving GXR will begin dosing at 1 mg/d (days 1-7). Dosages will escalate to 2mg/d (days 7-21) and 3mg/g (day 21- onwards). Please see Appendix 5 for titration and updated taper schedule. Identical placebo tablets will be used. All guanfacine and placebo tablets will contain riboflavin in order to ensure compliance

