Medical management (MM) & contingency management (CM) for treatment adherence: The primary focus of the MM protocol¹³⁴ is to assist clinicians in providing educational support strategies for maintaining medication adherence. It was designed for delivery in a primary care setting and as such is a suitable platform for use in outpatient clinical trials assessing new medications for alcohol¹³⁵¹³⁷. Primary goals include promoting compliance via psycho-educational methods as well as encouraging participation into self-help programs aimed at women¹³⁴. The initial session will be 3045 minutes followed by 10 minute follow-up sessions once per week. In addition, all subjects will receive CM providing participants with the opportunity to increase chances of winning variable dollar prizes at study completion for kept appointments. See Human Studies Section for full details of gender-specific recruitment goals (1.2) & CM protocol (4.1.3). **3.5.3 Outpatient Assessments:** Primary Outcomes: All participants will be required to provide a urine and breathalyzer screen at each appointment. In addition, the Time-Line Follow-Back Interview¹³⁰ will be used to assess all alcohol and nicotine use in the previous 90 days at baseline and weekly during the 10 week treatment trial. Primary alcohol use outcomes will be: (1) time to initial drink and heavy drinking (men: ≥ 5 drinks; women: ≥ 4); (2) frequency: the total number of days of alcohol use; and (3) quantity: the average amount of alcohol use (no. of drinks) per occasion. Subjects will be considered drop-outs if they receive two phone calls and two letters inviting them to return. We will attempt to assess these early terminators at the time of discontinuation, at the 10 week termination point, and at the follow-up period. These women will be withdrawn from the study but considered in the intent-to-treat efficacy analyses. Secondary Outcomes: The following measures will be administered upon admission and twice weekly to assess the effects of GXR on craving, anxiety, mood, stress and regulation: AUQ; STAI; BDI; POMS-Bi; PSS; DERS; BIS-11 and Stroop. Data Safety: The following measures will be assessed: (i) Sitting and standing vital signs: every 15 minutes for one hour (ii) Liver function tests, glucose and Complete Blood Count (CBC): weeks 4 and 8 for abnormal values (iii) Systematic Assessment of Treatment Emergent Events (SAFTEE): every week to assesses the severity and duration of potential physical or health problems. Adverse events will be documented according to the criteria outlined in the Human Subjects section 6.0. (iv) Blood draw to assess

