Aim1: To evaluate the safety and tolerability of GXR (3mgs/day) in women with Alcohol Use Disorder (AUD). All potential adverse effects from both treatment groups were recorded twice weekly and classified. Descriptive statistics are displayed in a frequency table.

Aim2: To determine the preliminary efficacy of 10-week GXR (3mgs/day) versus PBO treatment on outcome measures in women with AUD: Linear Mixed Effects (LMEs) models were used to analyze data from the intent-to-treat sample where, for all Dependent Variables (% no. of heavy drinking days, % no. of days abstinent, % drinks consumed on any one occasion, alcohol craving, depressive symptomatology, anxiety and emotion regulation), the Between Group Factors of Group (GXR, PBO) and Within Group Factors of Time-points (12-weeks), represented the Fixed Effects and Subjects represented the Random Effects. Demographic and drug use variables differing between Treatment Groups and associated with the Dependent Variables were entered as covariates into the models and a Compound Symmetry covariance structure was applied to the model. Descriptive statistics were additionally conducted on % no. of negative urines collected across the trial.

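### SAP Aim 2 sets a 12-week time factor for a 10-week treatment, so a Group effect averaged over all points may take in points outside treatment, and the baseline value of each outcome is not assured a place in the model

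*Combined protocol and SAP*

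**What the plan says.** The Statistical Analysis Plan states the purpose of Aim 2 as "To determine the preliminary efficacy of 10-week GXR (3mgs/day) versus PBO treatment". Later in the same sentence, the model for all seven listed outcomes has Group as the between-subject factor and "Within Group Factors of Time-points (12-weeks), represented the Fixed Effects and Subjects represented the Random Effects". The 12 points are not listed. No Group x Time term is mentioned, and no contrast is named as the one carrying the efficacy claim.

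The covariate rule reads: "Demographic and drug use variables differing between Treatment Groups and associated with the Dependent Variables were entered as covariates into the models".

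The protocol's stated schedules all run to 10 weeks:

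- Procedures, Outpatient procedures: "All AUD women will be required to attend two outpatient visits per week for 10-weeks".
- Outpatient Assessments, Primary Outcomes: the drinking calendar interview (TLFB) covers use "in the previous 90 days at baseline and weekly during the 10 week treatment trial".
- Follow-up interviews: one interview, 30 days after treatment ends.

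The taper complicates the end of treatment. Outpatient procedures says "In week 10 of treatment a 12-day taper schedule will be implemented", and Dosing adds "Please see Appendix 5 for titration and updated taper schedule". That appendix is not in the text available for this review.

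**The concern.** Ten weekly treatment points cannot fill a 12-week factor. Either the number is wrong, or at least some points lie outside the 10 treatment weeks. In a model with Group and Time-points as fixed effects and no stated interaction, the Group effect is an average over all the points. A point before treatment carries no drug effect in expectation, and a point after treatment carries only what has persisted. Averaging them in pulls the estimate toward zero and costs power in a trial of 60 women. Baseline TLFB also covers 90 days, whereas each treatment point covers a week, so it is not a like-for-like level of the time factor.

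The natural use of baseline is as a covariate, but the SAP's rule lets a variable in only if it is demographic or drug-related, differs between the groups, and is associated with the outcome. Baseline drinking might qualify if the arms happened to differ. Baseline craving, depressive symptoms, anxiety and emotion regulation are neither demographic nor drug use variables.

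**Working it through.** **1. Counting the points.** The documents give no derivation of 12, so I tried to build it from the schedule.

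- Weekly treatment points: 10.
- Baseline + 10 weeks: 11.
- Baseline + 10 weeks + 30-day interview: 12 points, but not 12 weeks, and two lie outside treatment.
- Running on through the taper: a 12-day taper starting on day s ends on day s + 11. Week 10 is days 64-70, so the last day falls on days 75-81. That is week 11 for starts on days 64-66 and week 12 for starts on days 67-70. A taper finished by day 70 would have to start on day 59, in week 9.

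No stated schedule yields 12 treatment weeks. Twelve is reached only by adding points outside the 10 weeks.

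**2. Dilution with complete data.** With equal weights, the 12-point average is (10 × D + a + b)/12, where D is the mean effect over weeks 1-10 and a, b are the effects at the two extra points. This does not require a constant effect within weeks 1-10.

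- a = b = 0: 10/12 = 0.833, a loss of 17%.
- a = 0, b = D/2 (baseline, and a follow-up keeping half the effect): 10.5/12 = 0.875, a loss of 12.5%.
- a = 0, b = D, or a = b = D/2: 11/12 = 0.917, a loss of 8%.
- 12 is a slip for 10: no loss.

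**3. What that could mean for power (illustration only).** The documents state no effect size, SD or power for Aim 2. Assume 30 per arm (60 women, 1:1 assumed), two-sided 0.05, and a standardised effect on the 10-week average of 0.7356, chosen to give 80% power (noncentral t, 58 df).

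| Multiplier | Power |
|---|---|
| 1 | 0.800 |
| 11/12 | 0.728 |
| 10.5/12 | 0.688 |
| 10/12 | 0.646 |

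The table holds the SD fixed. Recomputing it for 12 points at within-woman correlation 0.3, 0.5 and 0.7 changes the last row only to 0.660, 0.653 and 0.649.

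**4. Early drop-out.** The protocol expects up to 30% to leave after the first few sessions. Assume 21 completers and 9 drop-outs per arm leaving after week 1, 2 or 3, a constant effect in weeks 1-10, none at baseline or follow-up, and a common within-woman correlation r of 0.3 to 0.7. With the same pattern in both arms, generalised least squares gives each observation of a woman with m points the weight 1/(1 + (m − 1)r). The retained share of the effect is

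sum of n × t/(1 + (m − 1)r), divided by sum of n × m/(1 + (m − 1)r),

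where n is the number of women with that pattern and t is the number of treatment points among their m points. Completers have m = 12 and t = 10.

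- Drop-outs not seen again, leaving after week 1 (m = 2, t = 1), r = 0.7: (210/8.7 + 9/1.7)/(252/8.7 + 18/1.7) = 29.43/39.55 = 0.744, a loss of 26%.
- Drop-outs not seen again, leaving after week 3 (m = 4, t = 3), r = 0.3: (210/4.3 + 27/1.9)/(252/4.3 + 36/1.9) = 63.05/77.55 = 0.813, a loss of 19%.
- Drop-outs also seen at week 10 and at follow-up, as the protocol says will be attempted: leaving after week 1 (m = 4, t = 2), r = 0.7 gives 29.94/40.58 = 0.738, a loss of 26%; leaving after week 3 (m = 6, t = 4), r = 0.3 gives 63.24/80.21 = 0.788, a loss of 21%.

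Power across these settings is 53-62% if drop-outs are not seen again and 54-59% if they are seen at both later points. A 10-week model with the same early leavers not seen again has no dilution and 71-79% power.

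**5. Baseline as a covariate.** The standardised effect becomes 0.7356/√(1 − c²), with c the correlation between baseline and the 10-week average, on 57 df. For c = 0, 0.3, 0.5 and 0.7, power is 0.800, 0.835, 0.899 and 0.975.

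**The case against.** The harm depends on two things the SAP does not establish: that points outside treatment are among the 12, and that the claim rests on a Group effect averaged over them. If 12 is a typing error, nothing is lost. If the test was a Group x Time contrast limited to weeks 1-10, baseline is an ordinary reference level and the dilution does not arise. Appendix 5 might explain weeks 11 and 12, in which case those points may still carry part of the effect. For the drinking outcomes, calendar recall might also recover weeks that drop-outs missed, bringing the loss back to about 17%. All of this stands, and it is why the size is given as a range that includes zero.

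It does not remove the contradiction. Even if Appendix 5 accounts for two more weeks, they lie beyond the 10-week treatment that the SAP names.

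Three stronger readings are tempting and not supported:

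- A reader might infer that the efficacy estimates are known to be diluted. The documents do not say what the 12 points are.
- A reader might build a larger loss by supposing that drop-outs are seen again only at follow-up. The protocol plans to attempt an assessment at week 10 as well.
- A reader might object that "a Compound Symmetry covariance structure was applied to the model" inflates false positives. That would concern a Group x Time test, which the SAP does not state, and would depend on assumed correlations. The structure does not harm the Group main-effect test.

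**Conclusion.** The 10-week and 12-week figures contradict each other within one SAP sentence, and every stated schedule supports 10. That much is certain, subject to Appendix 5 being unavailable. The consequence is conditional: no loss if 12 is a slip or the contrast is confined to weeks 1-10; up to 17% dilution of an averaged Group effect with complete data and two null points; roughly 19-26% with early drop-out, on assumed timing and correlation. The week counts fix only the 10/12 ratio, given two null points with equal weight. Every power figure rests on assumed inputs.

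The baseline gap is a separate weakness. It holds whichever meaning of 12 is right, because the covariate rule turns on observed group differences. The point should be corrected, since one model serves all seven Aim 2 outcomes and the remedy is cheap.

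**What to change.** - Set the efficacy time factor to the 10 weekly treatment intervals. If 12 is intended, identify each point as baseline, treatment, taper or follow-up, and limit the efficacy contrast to the treatment weeks.
- Enter the baseline value of each outcome as a covariate regardless of observed imbalance, and not as a level of the time factor.
- Analyse the 30-day follow-up and any weeks after week 10 separately.
- Reconcile the 10-week treatment period, the 12-day taper placed in week 10, Appendix 5 and the 12-week factor before assigning taper days to an analysis window.
- The SAP is written in the past tense. If the data had been seen, label the whole revised model post hoc, not only the contrast.

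The cost is revised wording, a re-run on existing data, and one degree of freedom per outcome for the baseline term. The gain from that term is small where baseline correlates weakly with on-treatment values, which is possible for a 90-day drinking baseline set against weekly drinking.

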Human Subjects: This study aims to recruit 60 women seeking out-patient treatment and who meet current DSM-V criteria for moderate-to-severe alcohol use disorder (AUD). In addition we will recruit a separate small sub-sample of 10 women who are nicotine dependent and treatment-seeking, but do not meet criteria for AUD. On the basis that up to 30% of participants may drop-out of treatment after the initial few sessions^{109, 110}, we anticipate that at least 49 AUD women will run through the laboratory stress challenge. AUD women enrolled in this study will predominantly come from low socio-economic backgrounds in Suffolk County, Long Island. In addition the Health Science Center at Stony Brook Hospital comprises a dedicated Comprehensive Psychiatric Emergency Program (CPEP) which sees 6200 patient visits per

year, with referrals commonly being made for persons with alcohol abuse and mental illness. Each patient is evaluated by a psychiatrist with regard to present episode, past psychiatric history, substance abuse, family and psychosocial context, medical history, and current status. Mental status and physical examinations are also made and potential referrals filtered into the appropriate research programs. CPEP additionally has close links to 67 alcohol and substance use disorder facilities across Long Island, including 8 detoxification centers, 6 inpatient clinics, and 7 residential programs all in close proximity. In relation to the racial and ethnic background of the women typically referred to CPEP: 70% are Caucasian (and of those 10% are Hispanic) and 30% are African American. As a result, we expect that the projected demographics of our sample will follow the above race breakdown. Subjects will be recruited by the research team based in the Department of Psychiatry at Stony Brook, through general practitioners at Stony Brook hospital and advertisements in local area newspapers, radio and other print media as well as study flyers posted in community buildings in the Suffolk County area. We propose the following strategies to encourage women into the study:

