Recruitment & retention strategies tailored to women: **a)** Research indicates that community involvement plays an integral role in recruiting both women and ethnic minorities into clinical trials 142. In view of the proposed study, both [name] and the recruitment teams based at Stony Brook Psychiatry, will maintain regular contact with Suffolk County Communities of Solution and the Long Island Counsel of Alcohol and Drug Dependence. Regular meetings will be organized with objectives to work closely with prominent community leaders within the local area in order to devise culturally appropriate community-based participatory recruitment strategies encouraging women from ethnic minorities into our research projects. **b)** As women are more likely to seek care for alcohol use disorders within primary care settings143, we intend to focus recruitment efforts within medical health centers and approach a local network of general practitioners within Stony Brook hospital willing to inform women of our treatment program; **c)** Treatment will predominantly be focused on psychoeducational techniques directed at the needs of women, incorporating issues associated with stress, self-esteem, domestic violence, parenting, caregiving status, trauma, anxiety, negative mood and eating; **d)** As research has shown that programs which allow women to bring their children have higher rates of retention and are a predictor of better treatment outcomes, we will encourage women to bring their children with them to all visits. The outpatient department at Stony Brook, employs several research assistants and associates with additional expertise in running developmental research protocols, and the Child and Adolescent Psychiatry Department is well-equipped to offer onsite child-care assistance while mothers complete the treatment visits with clinical staff; **e)** we have budgeted for local transportation if required146; The following inclusion / exclusion criteria will be required for eligibility:

Addendum as per COVID -19 CDC guidelines:

All potential / ongoing participants will be screened for exposure to the COVID-19 virus using the CDC guidelines below:

1. *Have you traveled to the following places in the last 14 days?*
-China, Iran, Japan, any country in Europe or South Korea? (Note that all level 3 and level 2 countries/regions listed on the CDC website are included; CDC is checked regularly for updates.

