2. *Have you had any of the following symptoms in the last 14 days without confirmation it was NOT COVID -19*

A flu positive test result or chronic medical condition? Fever greater than 100.4 deg F? Cough, difficulty breathing, sore throat?

3. *In the past 14 days have you lived with, visited, cared for, or been in a room for a prolonged period of time with someone who is under investigation or has been confirmed for COVID-19/ Corona virus infection?*
 - Any YES response the subject will be asked to make an appointment for a later date and will be directed to the Coronavirus Hotline/phone triage center set up at Stony Brook Hospital [contact].

Any and all subjects need to be asymptomatic for all scheduled visits ongoing through the study. Safe distancing practices will be implemented at all in office meetings, should they occur. Virtual visits will be utilized for any visits as the need sees fit.

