Participant will then administer the first dose of study medication or virtual media visit. Questionnaires and surveys will be conducted and timeline follow back will be obtained. Sit stand blood pressure recordings will be taken at the end of this intake. Appointment for the weekly virtual visits will be scheduled.

Medication

At a second intake appointment participants will meet with the study MD, and once cleared begin the first dose of Guanfacine or placebo. They will be randomly assigned to either GXR (3mgs) or PLA, and will receive the exact amount of medication until their next visit, provided in unit/dose containers and labeled with the time and date to facilitate appropriate dosing. Riboflavin will be added to the medications and blood plasma assessed for medication levels every four weeks to ensure compliance¹³¹. The use of extended release GXR will also necessitate the use of only 1 tablet per day, increasing likelihood of adherence

ALL SESSIONS:

SAFETY GUIDELINES FOR THE COVID-19 VIRUS DURING:

WEEKLY STUDY VISITS 2 x per week – all virtual:

All assessments will be performed by virtual visit over a secured media site. Using ZOOM with end to end encryption. Subjects will be mailed via UPS with signature required: 1 BP monitoring kit, Urine toxicology cups, 1-week medication until titrations to the optimal dose of 3 mg of Guanfacine or Placebo; based on the blind randomization assigned by the pharmacist. Subjects will receive virtual tutorials from the research staff on the use of the BP monitor and utilization of the urine toxicology cups through zoom. Subjects will be monitored via virtual media during the use of these tools each visit. All adverse events to be reported and documented during these visits. Reported to study MD as needed and virtual visit with MD as needed. All SAFTEE documents will be administered and documented. One virtual visit each week will include medication management, with continued assessment of the subject during the COVID_19 crisis to insure that additional counseling is not needed.

Weekly Assessments include the following:

1. SAFTEE sheet – documenting any adverse effects

2. A series of short rating scales measuring: craving (AUQ), stress (PSS), emotion regulation (DERS), mood (POMS), anxiety (STAXI), depressive symptoms (BDI) and withdrawal symptoms (CIWA)
3. Timeline follow back (TLFB) – subject report of daily alcohol/drug use
3. Vitals – sitting to standing

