
medication levels: weeks 4 and 8 (v) urine test to ensure the participant is not pregnant: weeks 4 and 8.

SAFETY GUIDELINES FOR THE COVID-19 VIRUS DURING:

LAB SESSIONS:

Safe distancing practices to be implemented during the pandemic crisis. NO stress challenge labs will be initiated until the STATE OF NEW YORK is cleared by the CDC, or NIH from this current DISASTER CRISIS.

Laboratory Session: The laboratory challenge session will be conducted in the 10th week of outpatient treatment, when all participants have reached full dose. During the lab, subjects will be brought into the testing room at 1 PM following a smoke break to control for nicotine withdrawal if needed. A cotton ball will be placed inside the mouth to collect saliva, a blood pressure cuff and pulse oximeter used to periodically monitor vitals. After 10 minutes relaxation, baseline measures of alcohol craving, nicotine craving, anxiety, mood, HRBP and saliva will be collected -5 minutes prior to imagery exposure. Subjects will then be given headphones and asked to imagine the situation being described, 'as if' they were actively participating in it at that moment. The script (either stress or neutral) will be presented for exactly 5 minutes. All measures will be collected immediately following imagery (0) and again at +15 minutes and +30 minutes following imagery exposure. The Stroop task¹³⁸ will be administered at baseline and following imagery only. All saliva will be placed on ice immediately, prior to storing at -20. Participants will then be given a 1-hour break to relax, before repeating the procedure. All procedures will be identical, with the exception of the imagery presented (stress or neutral). The imagery order will be counterbalanced and neither the subject nor the investigator will know the order of imagery presentation prior to the study. Relaxation instructions will be provided to ameliorate any residual effects of imagery. Imagery script development, imagery training and relaxation techniques will be conducted in the week prior to the laboratory sessions (see Human Subjects Section 2.4). 3.7 Follow-up interviews: Face-to-face interviews will be conducted 30 days after outpatient treatment completion. Urine and breathalyzer screens and a daily assessment of alcohol use will be collected using the TLFB method¹³⁰

All 30 day follow-up interviews will be conducted over zoom.

STATISTICS

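### If enrolment spanned the move to virtual visits, the Aim 2 covariate rule keeps enrolment era out of the models, so a chance era imbalance between arms stays in the Group estimate

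*Combined protocol and SAP*

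**What the plan says.** **Base design.** Under Study sample the protocol states "This study aims to recruit 60 women seeking out-patient treatment". Under Procedures, "All AUD women will be required to attend two outpatient visits per week for 10-weeks". The recruitment section assumes physical attendance: "we will encourage women to bring their children with them to all visits".

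**COVID-19 updates.** The text added under Screening and intake is introduced as an update prompted by the pandemic, and the screening addendum covers both potential and ongoing participants. Under All Sessions the heading is "WEEKLY STUDY VISITS 2 x per week – all virtual", followed by "All assessments will be performed by virtual visit over a secured media site". The addendum placed before the eligibility criteria adds "Virtual visits will be utilized for any visits as the need sees fit". No date is given for the change, and no count of women enrolled before or after it.

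**Allocation.** The Medication and All Sessions sections describe random assignment to GXR or placebo, held by the pharmacist. They give no ratio, blocking or stratification, and nothing that would balance the arms over calendar time.

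**Analysis.** SAP Aim 2 fits linear mixed models with Group and Time-points as fixed effects and Subjects as random. Time-points are study weeks, not calendar dates. The only route for a further term is this rule: "Demographic and drug use variables differing between Treatment Groups and associated with the Dependent Variables were entered as covariates". Neither the SAP nor the protocol's Data Analyses Plan mentions enrolment period, visit mode or a pandemic sensitivity analysis.

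**The concern.** The modelled outcomes are drinking measures taken by calendar interview and self-report scales for craving, depressive symptoms, anxiety and emotion regulation. Their level could plausibly differ between women enrolled before the change and women enrolled after it, because the pandemic period differs and because the interview moves from clinic to video.

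If so, era is a prognostic baseline variable. In a sample of 60 the arms can differ on it by chance. The week factor does not absorb this, because week 1 is week 1 in either era. Nor does the subject random effect, which does not remove a difference between arms in the mix of women. The covariate rule does not help either: it tests only demographic and drug use variables, so era is left out even when the arms visibly differ on it.

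At stake is whether a reader of a small, preliminary trial can tell how far the Group estimate depends on who enrolled when.

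**Working it through.** The documents state no power, alpha, effect size, SD or era count for Aim 2, so there is no figure of the plan's own to reproduce. The check sizes the problem over a range.

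**Inputs**
- From the protocol: 60 women with AUD, randomised to two arms.
- Assumed: 30 per arm; no balancing by date; one era holding 20%, 35% or 50% of the women; an additive era effect *e* of 0.2, 0.5 or 0.8 SD; two-sided alpha 0.05; one summary measure per woman with within-era SD 1.

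**Step 1: chance imbalance.** With *K* of 60 women in one era, the number *k* of them falling in a given arm of 30 is hypergeometric. The between-arm difference in era share is *d* = *k*/30 − (*K* − *k*)/30. Its SD is √[p(1−p) × (2/30) × (60/59)].
- p = 0.5: √(0.25 × 0.0667 × 1.017) = 0.130
- p = 0.2: √(0.16 × 0.0667 × 1.017) = 0.104

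Exact tail probabilities:

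| Era split | at least 10 points | at least 20 points | at least 30 points |
|---|---|---|---|
| 20/80 | 33% | 10% | 0.2% |
| 35/65 | 59% | 10% | 3% |
| 50/50 | 44% | 20% | 2% |

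With 21 per arm (30% dropout: 60 × 0.70 = 42), the chance of 20 points or more runs from about 5% (20/80) to 22% (50/50).

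**Step 2: shift in the Group estimate.** Shift = *d* × *e*. The standard error is √(2/30) = 0.258 SD.

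| Imbalance | e = 0.2 | e = 0.5 | e = 0.8 |
|---|---|---|---|
| 20 points | 0.04 SD (0.15 SE) | 0.10 SD (0.39 SE) | 0.16 SD (0.62 SE) |
| 30 points | 0.06 SD (0.23 SE) | 0.15 SD (0.58 SE) | 0.24 SD (0.93 SE) |

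**Step 3: type I error given the imbalance.** The unadjusted test uses SE\* = √[(2/30)(1 + p(1−p)e²)], while the estimate is centred at *d* × *e* with SD 0.258. The rejection probability is 1 − Φ((1.96 SE\* − *de*)/0.258) + Φ((−1.96 SE\* − *de*)/0.258). Over the assumed era effects, with one era holding 30% or 50% of the women, it is 0.052 to 0.074 at 20 points and 0.055 to 0.125 at 30 points.

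**Step 4: what an era term changes.** Simulation with 20,000 allocations, 30 per arm, 50/50 split:

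| Era effect | SE without era | SE with era | Reduction | Type I error without / with |
|---|---|---|---|---|
| 0.5 SD | 0.266 | 0.260 | 0.006/0.266 = 2.3% | 0.048 / 0.048 |
| 0.8 SD | 0.277 | 0.259 | 0.018/0.277 = 6.5% | 0.049 / 0.050 |

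The mean estimate is about 0.00 with and without the term. With the term in the model, an additive era shift no longer enters the Group estimate at any imbalance.

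**The case against.** **Spanning is inferred.** The protocol's funding paragraph still describes the award as awaiting IRB approval, so the base text predates recruitment and does not show that any woman was seen in person. The inference rests on the update wording and the reference to ongoing participants. This objection stands, and the point has to be conditional. A reader might take the documents to establish a mid-trial switch with sizeable groups on both sides; they do not.

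**Much of the change never reaches the models.** A reader might infer that home urine cups and disposable breathalyzers contaminate the Aim 2 results, or that the follow-up ("Face-to-face interviews will be conducted 30 days after outpatient treatment completion", later moved to Zoom) does. The SAP does not support that. Urine results are summarised descriptively, and breath results, vital signs and the 30-day follow-up are not among the dependent variables. The drinking interview and most of the scales appear in both the base and the virtual text. Anxiety is the exception: it is named as STAI in the outpatient assessments and as STAXI in the virtual list, and the documents do not say whether that is a change of instrument or a slip. What remains is period and interview mode.

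**The effect is small.** Average type I error is about 0.05 either way, and the precision gain is near nil for era effects of 0.3 SD or less. This stands, and it limits the weight of the point.

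**Some contrasts are immune.** For women wholly within one era, an additive shift cancels from a Group-by-Time contrast. The SAP names no interaction and no target contrast, so this protection cannot be assumed. It also fails for women on treatment when procedures changed, whose number is not given.

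**Era is one case of a wider weakness,** namely choosing covariates by observed arm differences. That is fair, but relaxing the rule would not admit era unless era is named.

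**Conclusion.** The point holds in conditional form and is minor. If enrolment spanned the change, the Aim 2 models as written cannot adjust for enrolment era, and whatever chance imbalance occurred stays in the Group estimate.

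On an assumed 30 per arm, an imbalance of 20 points or more arises in about 10% to 20% of trials and moves the estimate by 0.04 to 0.16 SD, or 0.15 to 0.62 of its standard error. The range depends on assumed era splits (20/80 to 50/50) and assumed era effects (0.2 to 0.8 SD), none of which the documents give. If nearly all women belong to one era, the effect disappears.

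The tempting stronger reading is that the change of visit mode biases the drug–placebo comparison. The documents do not support it. Assignment is described as random and blinded, and nothing ties arm to enrolment date, so the unadjusted estimate is unbiased over randomisations. What is lost is some precision, and protection against an unlucky allocation.

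**What to change.** 1. State the date on which the virtual procedures took effect, and tabulate enrolment era by arm.
2. If both eras are represented, include in every Aim 2 model a fixed indicator of whether the woman was randomised before or after that date, whatever the observed imbalance. A woman on treatment when procedures changed keeps her era at randomisation.
3. Do not adjust the Group effect for the mode of individual visits. Under "Virtual visits will be utilized for any visits as the need sees fit", mode is settled after randomisation and may reflect how the woman is doing.
4. The SAP is written in the past tense. If the models have already been run, report the era-adjusted fit beside the planned one as a labelled post hoc sensitivity analysis; it can no longer be called pre-specified.

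Cost: a sentence in the SAP, one degree of freedom per model, and a refit where results already exist. The only data needed are the randomisation dates and the date of the change.
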